### 14.4 INTERIM MONITORING AND ANALYSIS

#### Part 1

The accumulating safety and tolerability data will be reviewed by the IDMC (see **section 20.2**) after **twenty participants have reached the primary endpoint of the immunisation schedule (Week 26; Visit 9)**. The IDMC will make a recommendation to the statistical team should any modification to the analysis plan or statistical tables be required. An unscheduled meeting of the IDMC may be required at the request of the Principal

Investigator (see section 20.2), in which case the IDMC will make a recommendation about whether or not to continue further immunisations in the trial.

## 14.5 DATA ANALYSES AND PRESENTATIONS

Main analysis population will be Intention-to-treat population. Per-protocol population and Modified-Intention-to-treat populations will be considered if important differences between populations arise.

### 14.5.1 PARTICIPANT POPULATIONS

- **Intention-to-treat (ITT) population:** all participants randomised and given at least one vaccination in the trial
- **Per-protocol (PP) population:** all participants randomised and immunised with all scheduled vaccinations, and who completed the trial with no major protocol deviations
- **Modified-Intention-to-treat (MITT):** all participants randomised and given at least one immunisation in the trial (including those participants whose sample collection occurred outside the allowed windows)

### 14.5.2 PRIMARY AND SECONDARY IMMUNOGENICITY OUTCOMES

All mucosal and serum samples will be screened for antigen specific antibodies IgG (and IgA). The absolute levels of antibody in samples that are found to be positive will be determined using a standardised and quantitative ELISA developed in [name]'s laboratory at Imperial College London. In this sandwich capture ELISA, the Ab of interest is captured by the relevant target antigen and then detected using a labelled isotype specific secondary Ab. An estimate of the concentration of Ab in the sample is calculated by interpolation relative to a standard curve based on titration of purified human standards IgG or IgA captured by anti-human kappa/lambda-specific antibodies.

The number of 'responders' in each assay will be presented by time-point and group as a proportion with 95% confidence interval. A 'responder' will be defined as a participant in whom a response was detected in two weeks after the final vaccination immunogenicity sample. A positive result will be defined relative to a pre-defined cut-off threshold value and assays will be validated using predefined thresholds based on the responses to positive and negative control stimuli. More information on the assay and definition of positive results will be supplied in the LAP. Titres of antigen specific antibodies will be described by time-point and group, and compared using rank tests where appropriate.

### 14.5.3 EXPLORATORY IMMUNOLOGICAL ASSESSMENT OUTCOMES

Exploratory immunological assessment outcomes will include evaluation of the proportion of individuals with systemic HIV-specific neutralising antibody responses (breadth and magnitude), the characterisation of non-neutralising antibody function including Antibody Dependent Cellular Viral Inhibition (ADCVI), Antibody dependent viral capture and aggregation assays, and assessment of anti-vector mediated immune responses i.e. anti-

MVA-CN54 and anti-Ad4-EnvCN54 antibody responses. CN54 gp140 specific antibody isotope responses (IgG1-4 and IgA) will be analysed and compared between vaccine groups.

#### **14.5.4 SAFETY OUTCOMES**

The AEs will be coded using MedDRA. If a participant reports the same event more than once then the worst severity and worst relationship to trial vaccine will be taken. Discrepancies between diary card and CRF reports will be queried by the monitor if unclear. It is assumed that the grade assigned by the clinician is more accurate, and this will be the grade reported in the tables. If the diary card grade is worse, this will be foot noted.

Safety outcomes will be reported overall with proportion and 95% confidence interval, and by group and time-point, and by relationship to study product, and method.

For the primary analysis of safety and tolerability endpoints (as defined in section 14.2), results will be expressed as a proportion with confidence interval.

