Group selection	
Part 1:
 
Participants will be recruited and randomised into groups A-H with an oral and I.M placebo control (dependent on treatment allocation). This will be a participant blinded study where the participants are blinded to the group and dosing regime to which they are assigned. The laboratory undertaking immunological analysis will also be blinded to group and dosing regimen to prevent bias in analysis.
 
Part 2:
 
Participants will be randomised to the groups chosen for expansion. If only one group is expanded, there will be no randomisation. Participants will be blind to the vaccine regime group to which they have been assigned. The laboratory undertaking immunological analysis will also be blinded to group and dosing regimen to prevent bias in analysis.

Summary Information Type	Summary Details
Number of Participants to be Studied	
The study will enrol 48 participants to Part 1 and 12 participants for Part 2.
 
In Part 1, n=6 participants per group will be randomised to groups A-H.
 
In Part 2, n=6 participants will be vaccinated to the best responding regimes.
 
Recruitment will select potential participants who are willing to undergo serial

	blood draws. Additional participants may be enrolled to replace any early withdrawals.
Duration of Study Participation	Participants will be screened up to 90 days before the first vaccination and will be followed up for 24 weeks after the last vaccine administration. Excluding screening, participants will attend for 11 visits in 48 weeks.
Evaluation for Inter-Current HIV Infections	Participants will be tested for HIV according to the Trial Assessment Schedule (Table 2). Test results will be interpreted according to a pre-determined diagnostic algorithm. Should one or more serological HIV test(s) post-vaccination be positive, a nucleic-acid-based HIV test will be performed (if clinically indicated) to distinguish a true HIV infection acquired through exposure in the community from HIV seropositivity due to the vaccine-induced antibody response. HIV testing at additional time points may be performed upon request of the volunteer and Principal Investigator or designee as medical or social circumstances warrant.
Organisation	The Coordinating Center will be the Group of Mucosal Infection & Immunity at ICL. Drafting of the SAP will be lead by the Surrey Clinical Research Centre.

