**TABLE 3: SOLICITED ADVERSE EVENTS**

Type	Event
Local AEs (Immunisation site)	Pain Tenderness Erythema / Discolouration Warmth Itching Swelling
Systemic Clinical AEs	Abnormally raised temperature Chills / rigors Myalgia / flu-like general muscle aches Malaise Excess fatigue Headache Nausea / Vomiting Abdominal Pain Diarrhoea Sore throat

The events will be graded according to **Appendix 1**.

**Relationship to the product**, the assumption is that any of these solicited events starting within 7 days of an immunisation are at least possibly related. If the onset is beyond 7 days, the event will be recorded on the adverse event CRF and a relationship determined by the investigator or delegate.

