**TABLE 4 TYPES OF ADVERSE EVENTS AND DEFINITIONS**

Type of Event	Definition
Adverse Event (AE)	
Any untoward medical occurrence in a patient or clinical trial subject to whom a medicinal product has been administered including occurrences that are not necessarily caused by or related to that product.
 
The Principal Investigator will use the following criteria when deciding whether to report a laboratory parameter that falls outside the normal range according to the local laboratory guidelines as an adverse event:
 
 
- If it is clinically significant and Grade 1 (or above) according to the grading system in Appendix 1 the abnormal result will be recorded as an AE
 
-
 

Adverse Reaction (AR)	
Any untoward and unintended response to an investigational medicinal product related to any dose administered.
 
'Related' means possibly, probably or definitely as defined below.
 
All solicited adverse events which start within 7 days of a vaccination will be automatically classified as an adverse reaction.

1 An abnormal result will be deemed to be clinically significant if any of the following apply:

- The test result is associated with relevant accompanying symptoms
- Additional diagnostic tests or medication are indicated

- As a consequence of the test result, an immunisation is delayed or further immunisations are discontinued
- The investigator considers the result to constitute an adverse event for any other reason

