##### *Safety and Tolerability:*

- Proportion of participants with severe or greater (Grades 3-4) adverse reactions during the study
- Proportion of participants with vaccine-related serious adverse events (SAEs) throughout the study period

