12.2.2 Safety and Tolerability

Safety data analysis will be based on the safety population and procedure described in here is applicable for both part 1 and part 2.

The following table illustrates the schedule used in capturing and monitoring adverse events.

Visit		1	2	3	4	5	6	7	8	9	10	11
Study Month		M0			M3			M6				M12
Study Week		W0	W1	W4	W12	W13	W16	W24	W25	W26	W28	W48
Study Day		D0	D7	D28	D84	D91	D112	D168	D175	D182	D196	D336
Visit Windows (Days)	-90		±1	±2	(±7/+14)	±1	±2	(±7/+14)	±1	±2	±2	±14
Solicited Adverse Events		X ⁶	X		X ⁶	X		X ⁶	X			
Review Solicited AE on diary card			X			X			X			
Unsolicited Adverse events		X ⁶	X	X	X ⁶	X	X	X ⁶	X	X	X	
Serious adverse events		X	X	X	X	X	X	X	X	X	X	X

Information on three different types of adverse events/reactions were collected at various timepoints, particularly pre- and post- vaccination on the day, throughout the study namely the serious, solicited, unsolicited adverse events. Adverse events/reactions are categorised both in terms of the severity (graded 1-4) and relatedness to the IMP (unrelated, unlikely, possible, probable, and definitely related).

As part of the safety and tolerability aspect of the primary endpoint reporting, the following will be reported,

- The frequency and percentage of participants with vaccine-related serious adverse events (SAEs) throughout the study period
- The frequencies and percentages of participants with severe or greater (Grades 3-4) adverse reactions at each time point during the study will be reported.

In addition to that, the frequencies and percentages of all adverse events/reactions separately for solicited, unsolicited and in combination will be reported and grouped by time point (separately for each time points and for all time points combined), severity

(graded 1-4) and relatedness (unrelated, unlikely, possible, probable, and definitely related). Whenever possible results will be split between arm 1 and arm 2 in part 1.

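### The repeat-event rule in Protocol 14.5.4 takes worst severity and worst relationship separately, so with 'same event' undefined it can count a Grade 3-4 adverse reaction that no single episode supports

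*Protocol*

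**What the plan says.** The primary tolerability endpoint (Protocol 14.2.1) is "Proportion of participants with severe or greater (Grades 3-4) adverse reactions during the study". Protocol 13.1, Table 4, makes an event a reaction when its relationship is possible, probable or definite, and adds: "All solicited adverse events which start within 7 days of a vaccination will be automatically classified as an adverse reaction". For later onsets of the same symptoms, the text under Table 3 in Protocol 12.3.4 says: "If the onset is beyond 7 days, the event will be recorded on the adverse event CRF and a relationship determined". One symptom can therefore be related at one report and unrelated at another in the same participant.

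Protocol 14.5.4 first provides for MedDRA coding. It then gives the rule for repeats: "If a participant reports the same event more than once then the worst severity and worst relationship to trial vaccine will be taken". Next come sentences on diary-card and CRF discrepancies, and the section ends: "For the primary analysis of safety and tolerability endpoints (as defined in section 14.2), results will be expressed as a proportion with confidence interval". The primary analysis is not exempted from the repeat rule, and the same event is not defined.

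SAP 12.2.2 says: "The frequencies and percentages of participants with severe or greater (Grades 3-4) adverse reactions at each time point during the study will be reported". It also asks for all adverse events and reactions by severity and relatedness, for each time point and for all time points combined. It gives no rule for repeat events.

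**The concern.** A Grade 3-4 adverse reaction requires severity and relatedness in the same occurrence. Two separate maxima over several occurrences break that link.

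Suppose a participant has a Grade 1 headache the day after a dose, which is automatically a reaction. Weeks later the participant has a Grade 3 headache with no apparent diagnosis, judged unlikely to be related. If both are the same event because they share a term, the merged record is Grade 3 and at least possibly related. The participant then enters the numerator of a primary endpoint without having had a severe reaction.

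What is at stake is the accuracy of a primary proportion reported by group, where the Protocol summary states: "In Part 1, n=6 participants per group will be randomised to groups A-H". The tables pooled over all time points are exposed in the same way, because records must be collapsed there and Protocol 14.5.4 holds the only rule for doing so.

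**Working it through.** **1. The plan's own figure for precision.** Neither document gives a figure for the repeat rule. The nearest is Protocol Table 7, the 95% Clopper-Pearson intervals at n=6. With x events in n, the lower limit is the 0.025 quantile of Beta(x, n−x+1) and the upper limit is the 0.975 quantile of Beta(x+1, n−x). Rows 1 to 6 reproduce to the rounded percent. Row 0 does not: 1 − 0.025^(1/6) = 45.9%, against the printed 39%. A one-sided 95% limit, 1 − 0.05^(1/6) = 39.3%, would explain the printed value, but row 6 (54%) is two-sided. Nothing below depends on this, and I use 45.9%.

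**2. The rule applied to one participant.** Records: (Grade 3, unlikely) and (Grade 1, possible).
- Separate maxima: Grade 3 and possible, so counted.
- Episode level (one record both Grade 3-4 and related): not counted.

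**3. Direction of the error.** There are 4 grades × 5 relationship categories = 20 record types, hence 20 × 20 = 400 ordered pairs.
- Severe and unrelated types: 2 grades (3, 4) × 2 categories (unrelated, unlikely) = 4.
- Milder and related types: 2 grades (1, 2) × 3 categories (possible, probable, definite) = 6.
- Pairs counted by separate maxima but not at episode level: 4 × 6 × 2 orders = 48.
- Pairs counted at episode level but missed by separate maxima: 0, since a record that qualifies on both attributes makes both maxima qualify.

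The 48 of 400 shows direction only. It is not a rate, because the pairs are not equally likely.

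**4. Effect of one such participant.** Group size is 6 in Part 1. The total is 48 + 12 = 60, ignoring replacements.

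| Denominator | Without | With one |
|---|---|---|
| 6 | 0% (0 to 45.9%) | 16.7% (0.4 to 64.1%) |
| 60 | 0% (0 to 6.0%) | 1.7% (0.04 to 8.9%) |

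**5. Scale, on assumed frequencies only.** Let q be the share of participants with such a pair. The documents do not give q. The expected number among 60 is 60q, and the chance of at least one is 1 − (1 − q)^60.

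| Assumed q | Expected among 60 | Chance of at least one |
|---|---|---|
| 1% | 0.6 | 45% |
| 2% | 1.2 | 70% |
| 5% | 3.0 | 95% |
| 10% | 6.0 | 99.8% |

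These rows show sensitivity to q. They do not estimate it, and the recording rule in Protocol 12.3.1 points towards low values.

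**The case against.** The strongest case on the other side has five parts.

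- **One event may mean one episode.** The sentences after the rule deal with diary and CRF reports of an event, so the rule may concern one episode reported through several sources or visits. No unrelated episode is then merged. This is a fair reading. The sentence before the rule, on MedDRA coding, supports the other one, and the text does not choose.
- **Reactions are already classified event by event.** Table 4, section 13.3.3 and Table 5 of the Protocol assign causality to each event, so the repeat rule could be a summary-table convention only. That is possible, but the rule sits in the section that governs the primary safety analysis, with no exemption.
- **Diagnoses replace symptoms.** Protocol 12.3.1 records the diagnosis where one is apparent. A severe headache in a recognised illness would normally be recorded as the illness, not as a headache. This stands, and leaves mainly undiagnosed severe symptoms.
- **The SAP reports by time point.** This stands for that table, where most such pairs fall at different time points. It does not protect the whole-study proportion or the pooled tables.
- **The error is conservative.** This stands: no reaction is hidden.

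A reader might go further and attach a rate. For example, assume five common symptoms, with 30-50% of participants having a mild related episode of each and 1-3% an unrelated Grade 3 episode. That gives 1 − (1 − 0.3 × 0.01)^5 = 1.5% to 1 − (1 − 0.5 × 0.03)^5 = 7.3% of participants falsely counted. The documents support none of these inputs. They also imply that 1 − 0.99^5 = 4.9% to 1 − 0.97^5 = 14.1% of screened healthy adults would have an unrelated Grade 3 episode recorded under one of these terms, and they ignore the recording of diagnoses.

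**Conclusion.** The point holds as a gap in the definition. On the same-term reading, the rule as written can produce a Grade 3-4 adverse reaction that no episode supports, and neither document prevents it. The bias runs upward only. One affected participant adds 16.7 percentage points to a group of 6, or 1.7 points to 60. The frequency is unknown and probably low.

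Three stronger conclusions might be inferred, and the documents do not support them:
- **The endpoint will contain false reactions.** That needs both the same-term reading and a participant with such a pair.
- **One or two such events would decide the trial's conclusion.** No threshold or between-group test is attached to this proportion, and Protocol 14.3 disclaims confidence about group differences. The hold and discontinuation provisions (Protocol 11.5 and 12.6) refer to events as they occur, not to this merged summary.
- **More reactogenic regimens will be penalised.** The mechanism could work that way, since a related episode is needed, but no reaction rates by group are given.

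This is worth correcting before the safety tables are produced, because it concerns how a primary endpoint is derived and the remedy is nearly free. It does not undermine the safety monitoring.

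**What to change.** In Protocol 14.5.4 and SAP 12.2.2:

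1. Define the same event. One workable definition is a single episode, with its own onset and resolution, reported through more than one source or visit. Within such an episode the worst grade and worst relationship can still be taken.
2. Derive the primary endpoint at episode level. A participant counts only if at least one single episode is both Grade 3-4 and related, meaning possible, probable or definite, or solicited with onset within 7 days of a dose.
3. In severity-by-relationship tables, including those pooled over time points, use the worst severity among related episodes.
4. Keep separate maxima across episodes for one-way descriptive tables only, and say so in a footnote.

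The cost is a short text change in each document and one programming rule. No new data are needed: onset and resolution dates and relationship are recorded under Protocol 12.3.1, and severity under 13.3.2. The downside is a slightly less conservative count if any such pairs occur.

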## 10.2 RANDOMISATION CODES AND & UN-BLINDING

This is a single-blind, randomised trial with placebo controls. Participants will be block-randomised centrally to the study groups shown in Table 1, using a computer-generated algorithm with a back-up manual procedure. Randomisation will be stratified on the basis of gender. All participants in Part 1 and Part 2 will be blinded to the vaccine regime group to which they have been assigned. The laboratory teams undertaking immunological analysis will also be blinded to group and dosing regimen to prevent bias in analysis. The clinical team will remain unblinded to the vaccine regime of trial participants throughout.

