### 12.3.4 SOLICITED LOCAL AND SYSTEMIC ADVERSE EVENTS

Various local and systemic adverse events are known to be associated with licensed vaccines, and are referred to as 'solicited adverse events'.

This information will be collected from all study participants on the day of immunisation and at the day 7 safety visit following each immunisation, through direct questions asked during a structured face to face interview and through examination according to the schedule.

Participants will also be asked to complete a diary card recording solicited adverse events that start from each immunisation until the day 7 safety visit.

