**Please note the list above is not an exhaustive list**

A member of the clinical trial team must sign all laboratory reports. In the event of an abnormality, an indication should be given whether or not the abnormality is clinically significant (and therefore gradable per Appendix 1), the date of review and the signature of the clinician reviewing the result.

The database and source documents should be kept in a secure location for 2 years after the last approval of a marketing application or until 2 years have elapsed since formal discontinuation of product development, and at least 25 years after the clinical trial has ended.

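### The primary Grade 3-4 reaction count uses the unblinded clinician's grade and only footnotes a worse grade from the blinded participant's diary; laboratory values also pass through that team's judgement before they can count

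*Protocol*

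**What the plan says.** The endpoint in protocol 14.2.1 is "Proportion of participants with severe or greater (Grades 3-4) adverse reactions during the study". Section 14.5.4 reports safety outcomes overall with a 95% confidence interval, and by group and time-point.

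On disagreement between diary card and CRF, section 14.5.4 sets three rules:

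- The monitor raises a query only where the disagreement is not clear.
- On which grade counts, the rule is: "It is assumed that the grade assigned by the clinician is more accurate, and this will be the grade reported in the tables"
- On a higher grade entered by the participant, the rule is: "If the diary card grade is worse, this will be foot noted"

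On blinding, section 10.2 says of participants: "All participants in Part 1 and Part 2 will be blinded to the vaccine regime group to which they have been assigned". Of the assessors it says: "The clinical team will remain unblinded to the vaccine regime of trial participants throughout".

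On the diary, section 12.3.4 says: "Participants will also be asked to complete a diary card recording solicited adverse events that start from each immunisation until the day 7 safety visit".

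On laboratory results, Table 4 in section 13.1 makes an out-of-range value an adverse event only if it is both clinically significant and at least Grade 1. Its footnote gives four alternative criteria for significance, the last being the investigator's own view. The note after the list in section 15.1.1 has a clinical team member sign each report, and for an abnormality "an indication should be given whether or not the abnormality is clinically significant (and therefore gradable per Appendix 1").

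SAP 12.2.2 tabulates Grade 3-4 reactions but does not address diary and CRF disagreement, so the protocol rule stands.

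**The concern.** The person whose grade enters the primary table knows the allocation; the person whose grade goes to the footnote does not. Most systemic symptoms in Table 3 (malaise, fatigue, headache, nausea, muscle ache) have no measurement behind them. Under Appendix 1 they are graded by how far they interfere with daily activity, which the participant knows directly. Where the two grades differ, the plan settles the primary count with the group-aware one.

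The laboratory route has a similar feature and a weaker safeguard. A value that meets the Appendix 1 limits for Grade 3 or 4 but is called not clinically significant never becomes an adverse event, and no footnote is required. It appears only in general laboratory summaries.

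What is at stake is how far the by-group safety proportions can be trusted. With 6 participants per group, one judgement can decide whether a group shows any Grade 3-4 reaction at all.

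**Working it through.** **1. Who grades, and with what knowledge**

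| Source | Knows group? | When recorded | Role in the primary table |
|---|---|---|---|
| Participant diary | No (10.2) | Immunisation to day 7 visit (12.3.4) | Footnote if worse (14.5.4) |
| Clinician grade | Yes (10.2) | Pre-dose, 60 min, day 7 visit (Table 2) | Counted (14.5.4) |
| Laboratory value | Significance called by a team that knows | Table 2 visits | Counted only if significant, at least Grade 1 and judged related (13.1, 13.3.3) |

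Section 14.5.4 takes the worst severity when the same event is reported more than once, yet does not do so when the worse grade comes from the diary.

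**2. Direction**

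Compare the plan's rule with counting the worse of the two grades. If the clinician's grade is equal or higher, the rules agree. If the diary is Grade 3-4 and the clinician's grade is lower, the plan does not count it. Against that comparator the plan's count is equal or lower. Against a diary-only count it can go either way. A participant leaves the count only if no other reaction of theirs carries a clinician's Grade 3-4.

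**3. The plan's own precision figures**

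Protocol Table 7 gives 95% Clopper-Pearson intervals for n = 6. The limits are the Beta quantile at 0.025 with parameters (x, n-x+1) and at 0.975 with parameters (x+1, n-x). Rows 1 to 6 reproduce: 0.4-64.1, 4.3-77.7, 11.8-88.2, 22.3-95.7, 35.9-99.6 and 54.1-100%.

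Row 0 does not. With x = 0 the upper limit is 1 - 0.025^(1/6) = 45.9%, not the printed 39%. The printed value matches a one-sided 95% exact limit, 1 - 0.05^(1/6) = 39.3%, or a Wilson limit of 39.0%. This is a separate error, but it affects the row a group falls into when its only counted participant is regraded. I use 45.9% below.

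**4. Effect of one regraded participant (number assumed)**

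| n | Worse grade counted | 95% CI | Clinician grade only | 95% CI |
|---|---|---|---|---|
| 6 (Part 1 group) | 1/6 = 16.7% | 0.4-64.1% | 0/6 | 0-45.9% |
| 12 (expanded group) | 1/12 = 8.3% | 0.2-38.5% | 0/12 | 0-26.5% |
| 60 (48 + 12) | 1/60 = 1.7% | 0.0-8.9% | 0/60 | 0-6.0% |

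**5. Chance that a group of 6 shows at least one counted reaction**

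Let p be the chance that a participant has a Grade 3-4 reaction by the worse grade, and d the share of such participants not counted under the clinician's grade. The chance is 1 - (1 - p(1-d))^6. The documents give neither p nor d, so both are varied.

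| p | d = 0 | d = 25% | d = 50% |
|---|---|---|---|
| 5% | 26.5% | 20.5% | 14.1% |
| 10% | 46.9% | 37.4% | 26.5% |
| 20% | 73.8% | 62.3% | 46.9% |

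Example: p = 10%, d = 50% gives 1 - 0.95^6 = 26.5%.

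**The case against.** The rule is pre-specified and disclosed, and several safeguards surround it.

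- The clinician does not grade in ignorance of the diary. Section 12.3.4 requires a structured face-to-face interview at day 7, Table 2 schedules diary review at that visit, and section 12.2.1 provides 24-hour cover. A clinician may correctly recognise over-grading.
- Unclear discrepancies are queried by the monitor.
- Table 4 makes any solicited event starting within 7 days an adverse reaction automatically, so relatedness cannot be used to remove it.
- Fever, redness and swelling have numeric limits in Appendix 1.
- Clinical significance has listed criteria, such as accompanying symptoms or a need for further tests, that many Grade 3-4 laboratory values would probably meet. The protocol summary (section 2) puts all routine laboratory data in the safety analysis, and the SAP lists laboratory summaries.

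All of this stands, and it narrows the point to subjective solicited symptoms and to laboratory values called not significant. It does not remove the point: the grade in the primary table is still set with knowledge of group, and a footnote changes neither the proportion nor its interval.

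A reader might infer more than the text supports:

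- That the rule can only lower the count. This holds only against a worse-of-two-grades rule; a clinician's higher grade is also the one counted.
- That the diary is discarded. Worse diary grades are footnoted and can be recovered.
- That the hold rule in section 12.6 is affected. Section 14.5.4 governs what is tabulated, section 12.6 does not refer to it, and no contradiction between them is shown.
- That a comparison of Ad4 with oral placebo is distorted. No safety contrast is specified. SAP 12.2.2 splits Part 1 results by arm where possible, and each arm contains both kinds of group.

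**Conclusion.** The point holds as an opportunity for bias in descriptive by-group proportions. The documents do not show that grades were changed because of group, or in which direction. One regraded participant is worth 17 percentage points at n = 6 and 8 at n = 12. The intervals overlap heavily, and no decision threshold is tied to the difference. These sizes rest on assumed numbers of regradings and, for the chance calculation, on assumed risks of 5-20%.

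The laboratory part has no footnote to fall back on, but its link to the endpoint is looser: a laboratory adverse event must also be judged related (section 13.3.3) before it is a reaction. Programmed grading would therefore make such values visible without altering the primary proportion.

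The change is cheap and worth making; it is not a threat to the trial as a whole.

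**What to change.** In protocol 14.5.4 and SAP 12.2.2:

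1. Report the proportion of participants with a solicited Grade 3-4 reaction, with its 95% confidence interval, by group, using the worse of the diary and clinic grades. Put the clinician-grade proportion beside it. Make the worse-grade version the primary definition or, at minimum, a pre-specified sensitivity table. Settle which before grades are tabulated by group.
2. Grade every post-vaccination laboratory value against Appendix 1 by program, and tabulate Grade 3-4 values by group whatever the clinical-significance call. Label this a supporting safety table that does not change the adverse-reaction endpoint.

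The cost is a few sentences and two tables. Diary and laboratory data are already collected, and the footnote rule already requires the two grades to be compared. The downside is that participant over-grading may raise the reported proportion, which is why both versions should be shown. One limit remains: under the worse-grade rule an unblinded clinician can still raise a grade, so the rule removes dependence on downgrading only. No rule on dosing or on holding immunisations is touched.
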